### **6.3 Exploratory objectives**

Company Confidential Information

Company Confidential Information

## **7 Statistical methods for safety and tolerability data**

All subjects within the safety analysis set will be included in the safety data analysis.

### **7.1 Variables**

Adverse events, vital signs (blood pressure, heart rate, body temperature), ECG intervals, clinical laboratory measurements, immunogenicity, hematology, blood chemistry as well as subject demographics, baseline characteristics, and treatment information.

### **7.2 Descriptive analyses**

#### **Subject demographics and other baseline characteristics**

All data for background and demographic variables will be listed by treatment group and subject. Summary statistics will be provided by treatment group.

Relevant medical history, current medical conditions, results of laboratory screens, drug tests and any other relevant information will be listed by treatment group and subject.

Demographic table will include a corresponding p-value for comparison of baseline values between BYM338 and placebo groups. T-test can be performed for continuous variables and chi-squared test for categorical variables. Demographic table will be generated for both sets of patients (completed/not completed treatment).

#### **Treatment**

Data for study drug administration (rescue medication) and concomitant therapies will be listed by treatment group and subject.

#### **Vital signs**

All vital signs data will be listed by treatment, subject, and visit/time, and if ranges are available, abnormalities (and relevant orthostatic changes) will be flagged. Summary statistics will be provided by treatment and visit.

### **ECG evaluations**

All ECG data will be listed by treatment, subject and visit; abnormalities will be flagged. Summary statistics will be provided by treatment and visit.

### **Clinical laboratory evaluations**

All laboratory data will be listed by treatment, subject, and visit/time, and if normal ranges are available, abnormalities will be flagged. A separate listing is provided presenting all parameters in a subject with any abnormal values. Summary statistics will be provided by treatment and visit/time.

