Observations of dose-dependent, transient, sub-clinical elevations of lipase and/or amylase have been identified in several studies in the bimagrumab clinical program. The biological explanation for this temporal rise in pancreatic enzymes seen in some individuals is not yet fully understood.

As of 1 September 2018 there have been two confirmed cases of acute pancreatitis among approximately 1038 participants administered bimagrumab. There is no known association among participants receiving bimagrumab between the temporary elevations in lipase and/or amylase and an increased risk for pancreatitis. However, to reduce the potential risk of elevated pancreatic enzymes to study participants, volunteers with elevated amylase and lipase will be excluded as per [Section 4.2](#).

Participants will be monitored throughout the study as detailed in the [Assessment schedule](#). Safety monitoring guidance for participants who experience elevated lipase and/or amylase during the study is provided in [Section 9.4](#).

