9.1 Adverse events

An adverse event (AE) is any untoward medical occurrence (i.e., any unfavorable and unintended sign [including abnormal laboratory findings], symptom or disease) in a patient or clinical investigation patient after providing written informed consent for participation in the study until the end of study visit. Therefore, an AE may or may not be temporally or causally associated with the use of a medicinal (investigational) product.

In addition, all reports of intentional misuse and abuse of the study treatment are also considered an AE irrespective if a clinical event has occurred. See [Section 9.6](#) for an overview of the reporting requirements.

The occurrence of AE must be sought by non-directive questioning of the patient at each visit during the study. AEs also may be detected when they are volunteered by the patient during or between visits or through physical examination finding, laboratory test finding, or other assessments.

Abnormal laboratory values or test results constitute AEs only if they fulfill at least one of the following criteria:

- they induce clinical signs or symptoms,
- they are considered clinically significant,
- they require therapy.

Clinically significant abnormal laboratory values or test results should be identified through a review of values outside of normal ranges/clinically notable ranges, significant changes from baseline or the previous visit, or values which are considered to be non-typical in patients with underlying disease. Investigators have the responsibility for managing the safety of individual patients and identifying AEs. Alert ranges for liver and kidney related events are included in [Appendix 1](#) and [Appendix 2](#), respectively. Other laboratory values to check are markers of muscle distress (CK, myoglobin) and pancreatic enzymes (amylase and lipase).

AEs must be recorded on the Adverse Events CRF under the signs, symptoms or diagnosis associated with them, and accompanied by the following information:

1. The severity:
 - mild: usually transient in nature and generally not interfering with normal activities
 - moderate: sufficiently discomforting to interfere with normal activities
 - severe: prevents normal activities
2. Its relationship to the study treatment:
 - Yes or
 - No
3. Its duration (start and end dates) or if the event is ongoing, an outcome of not recovered/not resolved must be reported.

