9.4 Lipase and amylase elevations

To ensure subject safety and enhance reliability in determining the potential for pancreatic events with bimagrumab, a standardized process for identification, monitoring and evaluation of pancreatic events should be followed ([Table 9-1](#)).

Table 9-1 Safety monitoring guidance for amylase and lipase elevations

Event	Follow up monitoring
Lipase and/or amylase < 3x ULN	
 • If asymptomatic, follow up at discretion of investigator. • If clinical symptoms (e.g., abdominal pain, nausea, diarrhea) suggest pancreatic involvement, re-check enzymes (amylase, lipase) and inflammatory markers (C-reactive protein) and consider pancreatic imaging (i.e., CT or MRI) to evaluate for presence of pancreatitis.
Lipase and/or amylase ≥ 3x ULN	
 • Re-check enzymes (amylase, lipase) and inflammatory markers (C-reactive protein) independent of presence of clinical symptoms. • Assess subject for clinical symptoms. • Conduct pancreatic imaging (i.e., CT or MRI) to evaluate for presence of pancreatitis. • Study drug interruption based on findings of additional assessments and at discretion of investigator.

Medically significant pancreatic events which are considered as serious adverse events (SAEs) should follow the **standard procedures for SAE reporting** as described in [Section 9.2](#). Every pancreatic event reported as an SAE should include a causality assessment of the event via exclusion of alternative causes (e.g., gallstones, co-medication).

An investigation of the pancreas needs to be followed up until resolution. A gastroenterology consult can be included at the investigator's discretion. All follow-up information, and the procedures performed, should be recorded in the appropriate CRFs.

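### The visible safety analysis pre-specifies no by-arm count of patients whose lipase or amylase ever reached the protocol's 3x ULN action threshold

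*SAP*

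**What the plan says.** **The signal.** Protocol 3.7.2 reports: "Observations of dose-dependent, transient, sub-clinical elevations of lipase and/or amylase have been identified in several studies". It adds that the "temporal rise in pancreatic enzymes seen in some individuals is not yet fully understood", and cites "two confirmed cases of acute pancreatitis among approximately 1038 participants administered bimagrumab", while stating that no link between the enzyme rises and pancreatitis risk is known.

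**The monitoring.** Protocol 8.1 explains the Week 2 visit by the need to monitor these two enzymes. Exclusion criterion 8d bars patients with a confirmed value of 2x ULN or more. In Table 9-1 (protocol 9.4), a value of 3x ULN or more leads to these steps among others: "Re-check enzymes (amylase, lipase) and inflammatory markers (C-reactive protein) independent of presence of clinical symptoms" and "Conduct pancreatic imaging (i.e., CT or MRI) to evaluate for presence of pancreatitis".

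**The analysis.** Laboratory values are endpoints of the secondary safety objective (protocol 2.2, SAP 1.3.2). For them, SAP 7.2 states: "All laboratory data will be listed by treatment, subject, and visit/time, and if normal ranges are available, abnormalities will be flagged". It adds a listing of all parameters for any subject with an abnormal value, and summary statistics by treatment and visit/time. Protocol 11.5.2 has the same flagged listing and by-visit summaries. In the visible safety text, numbers and percentages of patients are specified only for adverse events. On when a laboratory result becomes one, protocol 9.1 says: "Abnormal laboratory values or test results constitute AEs only if they fulfill at least one of the following criteria". The criteria are symptoms, clinical significance or need for therapy; none is a multiple of ULN.

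**The concern.** For a transient rise in some individuals, the natural safety question is how many patients in each arm ever reached the level at which the protocol acts. That is a per-patient, worst-value question. The planned summaries are per visit, the flags are set against the normal range rather than 3x ULN, and the per-patient table covers only events that qualify as AEs.

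A randomised placebo arm lets this trial separate a drug effect on these enzymes from background. If the count is not pre-specified, then the threshold, the handling of unscheduled values and the denominator would all be chosen after the data are seen. Pancreatitis itself will be too rare to inform: if the programme-wide proportion applied, 34 x 2/1038 = 0.07 cases would be expected on bimagrumab. The enzyme counts are what a trial of this size can describe.

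**Working it through.** **Inputs from the documents.** 34 patients per arm (protocol 11.7, SAP 1.4); thresholds of 2x ULN (exclusion 8d) and 3x ULN (Table 9-1). The documents give no expected rate of values at or above 3x ULN, so there is no stated figure to reproduce. Every rate below is an assumption used for illustration.

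**1. Can by-visit output give the per-patient count?** Assume 34 patients and 6 visits, with every value 0.6x ULN except one value of 4x ULN at each visit.

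- Case A: the same patient is high at all six visits. Patients ever at or above 3x ULN: 1/34 = 2.9%.
- Case B: six different patients are each high once. Patients ever at or above 3x ULN: 6/34 = 17.6% (exact 95% CI 6.8 to 34.5%).

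At every visit, in both cases:

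- mean = (33 x 0.6 + 4)/34 = 23.8/34 = 0.70
- SD = sqrt[(33 x 0.1² + 3.3²)/33] = sqrt(11.22/33) = 0.583
- median = 0.6, maximum = 4.0

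The 34 values at each visit are the same set in A and B, so no by-visit statistic can tell the cases apart. Even a by-visit count at or above 3x ULN would read 1/34 throughout in both. The per-patient figure needs each patient's maximum over time.

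**2. Does the AE table supply it?** Only in part. A value at or above 3x ULN with no symptoms, no therapy and no judgement of clinical significance is not an AE under protocol 9.1. Protocol 6.10 likewise speaks of enzyme elevations that meet AE criteria, which implies that some do not.

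**3. What would the missing table show with 34 per arm?** Exact (Clopper-Pearson) 95% intervals:

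| Patients at or above 3x ULN | % | 95% CI |
|---|---|---|
| 0/34 | 0 | 0 to 10.3 |
| 1/34 | 2.9 | 0.1 to 15.3 |
| 3/34 | 8.8 | 1.9 to 23.7 |
| 5/34 | 14.7 | 5.0 to 31.1 |

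The upper limit for 0/34 is 1 - 0.025^(1/34) = 10.3%. The chance of seeing at least one such patient is 1 - (1 - p)^34: 50% at an assumed true rate p of 2%, 83% at 5%, 97% at 10% and 99.9% at 20%. Against 0/34 on placebo, two-sided Fisher p is 0.053 for 5/34 and 0.025 for 6/34. The table would be descriptive, but it would carry information.

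**The case against.** **The data are not lost.** A reader might infer that the trial can give no per-patient rate. The documents do not support that: all laboratory values are listed by subject and visit, and a second listing gathers every parameter for any subject with an abnormal value. With 34 per arm the count is easy to make. What is missing is its pre-specification.

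**The tables need not look alike.** A reader might also infer that the arms would appear the same. SAP 7.2 does not itemise the laboratory statistics, but where the SAP does so for PK and PD data it includes SD and maximum. A by-visit maximum would reveal an outlier, though not how many patients had one. The rises might also cluster early, which a Week 2 summary could show.

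**Some rises will be AEs.** Protocol 9.1 names amylase and lipase among the values to check, and a result that prompts imaging may well be judged clinically significant. It would then enter the AE percentages. So the AE table may undercount; it is not certain to miss the rises.

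**Redaction.** Other safety evaluations is blacked out in both documents and may contain this table. Its absence from the plan cannot be asserted. Amylase and lipase are, however, classed as blood chemistry (protocol 8.6.6), and the laboratory paragraphs where one would look first are fully visible.

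**Other safeguards.** An independent DMC reviews unblinded safety data (protocol 10.4). That protects patients during the trial, but it does not define what the study report will tabulate.

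**Unscheduled values.** A Table 9-1 re-check that follows a value already at 3x ULN adds no patient to the 3x count. Only re-checks prompted from below 3x could, so this element is minor.

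**Conclusion.** The point stands as a cheap improvement to the reporting of a secondary safety objective in a non-confirmatory trial. The visible laboratory analysis pre-specifies no number and percentage of patients, by arm, at the protocol's own 3x ULN threshold. The planned by-visit summaries cannot supply it: the same output fits 2.9% and 17.6% of patients in the worked example.

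That conclusion rests on the visible text and on arithmetic. It does not depend on any assumed event rate, and the documents give no basis for predicting how many patients would be affected. Nor do they support calling this the most closely monitored laboratory risk, since liver monitoring (protocol 9.3, Appendix 1) is more elaborate. A reader might want the same treatment for the liver and renal categories, but that does not follow from this argument; liver events already have their own AESI and SAE classes.

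**What to change.** In SAP 7.2, under Clinical laboratory evaluations, add one table by treatment arm. For lipase and for amylase, and for either enzyme, take each patient's maximum post-baseline value as a multiple of ULN, unscheduled values included. Report the number and percentage at or above 2x ULN and at or above 3x ULN, with exact 95% confidence intervals and the between-arm difference with its interval. State the denominator (treated patients with at least one post-baseline value) and label the table descriptive. If the redacted Other safety evaluations text already contains this, a cross-reference is enough.

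The cost is one SAP paragraph and one table from data already collected, with small counts and wide intervals. It uses thresholds already in the protocol and changes no dose, monitoring or stopping rule.

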### **Adverse events**

All information obtained on adverse events will be displayed by treatment and subject.

The number and percentage of subjects with adverse events will be tabulated by body system and preferred term with a breakdown by treatment. A subject with multiple adverse events within a body system is only counted once towards the total of this body system and treatment.

### **Other safety evaluations**

Company Confidential Information

### **Immunogenicity**

All immunogenicity results will be listed by subject and visit/time.

## **7.3 Graphical presentation**

Figures may be created, as needed, to explore safety data trends.

## **8 Statistical methods for Pharmacokinetic/Pharmacodynamic interactions**

Scatterplots may be used to explore the relationships between systemic exposure to BYM338 and selected safety/PD endpoints. Other graphical exploration may be done as appropriate.

## **9 Statistical methods for biomarker data**

Company Confidential Information

Company Confidential Information
